4.2.5 Removal of Subjects from Study

In accordance with the Declaration of Helsinki and the Code of Federal Regulations, a subject has the right to withdraw from the study at any time for any reason without prejudice to his/her future medical care by the physician or the institution. Should a subject (or subject's legally authorized guardian/representative) decide to withdraw; all efforts will be made to collect and report the final visit observations as thoroughly and timely as possible. Subjects who withdraw from the study will not be replaced.

The primary reason for early termination and the date of termination will be recorded in the electronic case report form. Reasons may include:

Investigator Decision

If the subject experiences an adverse event and the Principal Investigator or Medical Monitor believes it is in their best interest to discontinue participation in the study, they will be withdrawn from the study.

Lost to Follow-up

When contact with the subject has been lost without completing the final visit assessment, and every attempt to contact has failed, the subject will be considered lost to follow-up. Attempted contact with the subject should include 2 attempted phone calls and the sending of a certified letter before the subject can be considered lost to follow-up. Final documentation regarding all attempts to contact the subject requesting their return for the final visit should be documented.

Withdrawal of Consent

The subject withdraws consent for participation in the study. Any method of contact with the subject in which they state they no longer want to participate in the study specific activities constitutes withdrawal of consent. When possible the reason for withdrawal will be documented.

Site Termination or Study Termination

A site or study may be terminated. When this occurs all subjects at the site will be withdrawn and documented as early termination. Reasons for site or study termination may include, but are not limited to the following:

- Administrative Concerns (e.g., inadequate subject enrollment, Investigator/institution non-compliance, change of business strategy, etc.);
- Safety Issues, including those due to non-compliance, which substantially affect the risk to benefit ratio of the study subjects at a site or for the study as a whole;
- Regulatory Body Mandate(s)

Other (which may include):

- Protocol deviation, noncompliance or violation
- Sponsor recommendation
- Device/index procedure failure
- Death

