5.2.2 Study Arm – Surgery with Intercostal Cryoanalgesia + standard POPM

If the subject is randomized into the Study Arm, the subject will receive one session of cryoanalgesia

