8.2.2 Protocol Deviations

The Investigator agrees to conduct the study in accordance with this protocol; however, protocol deviations may occur during the course of the study. Protocol deviations are events occurring during the conduct of the study which are not in compliance with the protocol and for which an amendment has not been granted. Protocol deviations can be committed by the Sponsor, the PI, or study subject. A deviation can be identified from a number of sources. Potential sources include, but are not limited to: a member of the PI's staff, the CRA during monitoring visits, or a member of the data management or statistical groups when entering or analyzing data. The PI or PI's representative are encouraged to contact the CRA or AtriCure as soon as possible upon observing a protocol deviation. Regardless of the source, it is crucial to document the deviation and record all corrective actions. Protocol deviations will be reported in the final report.

The process for capturing deviations will be detailed in the monitoring plan. The process will require that documentation describe the deviation, appropriate actions taken, and will be included in the study file for the respective PI and subject. The study site representative will be advised to record the deviation and relevant discussion with the Sponsor about the deviation in subject source documents.

Protocol deviations affecting the scientific soundness of the study or the rights, safety, or welfare of the subjects, will be reported by the PI, as required by the IRB.

Protocol deviations will be summarized and grouped into relevant categories for analysis and may include, but not be limited to, subjects who:

- Entered the study although they did not satisfy the eligibility criteria; or
- Developed withdrawal criteria during the study, but not removed.

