9.5 Analysis Populations

Intent-To-Treat (ITT) Population: The effectiveness, safety and health economics analyses will be based on the ITT population. The ITT Population is defined as all subjects randomized to either the Study Group or SOC Group and on whom the surgical index procedure is attempted (even if the index procedure is aborted).

Per-Protocol (PP) Population: A PP population may be defined for effectiveness and health economics and analyses. This population is defined by ITT population but without any major protocol violations, that is, those that could potentially bias the results.

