10.2.4 Reporting Adverse and Serious Adverse Events

The investigator (or designee) will record all AEs (both serious and non-serious and regardless of relationship) in the source documents. The Investigator at each site participating site is responsible for reporting AEs and SAEs to AtriCure only when they are related to the CryoAnalgesia index procedure or device. AEs related to the CryoAnalgesia procedure or device will be reported on the eCRF. The CRFs allow the investigator to indicate whether or not the adverse events are related to the device or index procedure.

- Use a separate Adverse Event Form to document each event
- The Adverse Event Form must be electronically signed by the Investigator

Note: It is the responsibility of the Investigator to inform their IRB of SAEs as required by their IRB procedures and in conformance with FDA requirements.

All Serious Adverse Events that are related to the CryoAnalgesia index procedure or device must be reported by the Investigator by submitting the AE eCRF to AtriCure within 10 days of becoming aware of the AE. An event determined by the Investigator to be life threatening or to have led to death should be reported within 24 hours.

The Investigator shall send a written report including a narrative description of the SAE to AtriCure within three (3) working days of the initial report. The Investigator should follow all unresolved SAEs

until the events are resolved, or the subject has exited the study or the AE is otherwise explained.

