APPENDIX 3 - RISK/BENEFIT ASSESSMENT

Clinical Risk/ Benefit Assessment

SUMMARY

The cryoICE™ CryoAnalgesia study is being undertaken to examine pain management in post thoracic procedures via intercostal cryoanalgesia. Subjects meeting the inclusion/exclusion criteria and undergoing unilateral thoracotomy cardiac procedures will participate in this study. The risks of participation are offset by the significant potential for clinical and functional benefits.

POTENTIAL BENEFITS

The potential benefit to study subjects outweighs the risks of participation in this study.

The benefits may include but are not limited to, the following:

- Clinical improvement - patients may experience improved post-operative pain control following minimally invasive heart valve surgery
- Functional improvement - patients may experience less post-operative pulmonary complications, less mental status changes, improved blood pressure and heart rate
- Overall advancement of medical and scientific knowledge - Information obtained from this study may further our understanding of peri-operative pain control following this surgical procedure and improve patient post-operative experience.

There may also be other benefits that are unforeseen at this time.

POTENTIAL RISKS

Risk Category: Minimal

Independent from this research study, the participant is already scheduled to undergo a minimally invasive heart valve surgical procedure via right mini-thoracotomy. All risks for this procedure will have been discussed with the surgeon and surgical consent will have been signed. Similarly, common anesthetic risks will have been discussed, and anesthetic consent will have been signed. The participant will be fully informed of the risks of this study. Possible adverse events may include, but are not limited to, the following.

Risks of Intercostal Cryoanalgesia with the cryoICE® probe:

Most frequent (occurring more than 10% of the time):

- Device Breakage
- Skin injury due to cryoablation minor damage of skin that would heal over time
- Intercostal muscle injury
- Permanent peripheral nerve damage resulting in difference in sensation not evident prior to surgery
- Failure to ablate peripheral nerve may result patient requiring pain management

Less frequent (occurring 1-10% of the time):

- Tissue perforation
- Tissue freezing

Rare (occurring less than 1% of the time):

- Injury to user
- Nitrous gas exposure to patient

There may also be other risks that are unforeseen at this time.

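### Section 4.2.5 permits exit from the study for device or index procedure failure after a one-session treatment, and nothing secures or handles the 48-hour values of those exited

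*Combined protocol and SAP*

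**What the plan says.** - **Reasons for exit.** Section 4.2.5 lists reasons for early termination to be recorded on the eCRF. Under its 'other' category come "Protocol deviation, noncompliance or violation", sponsor recommendation and "Device/index procedure failure". The list is permissive and gives no timing. Separately, if a subject has an adverse event and the investigator or Medical Monitor "believes it is in their best interest to discontinue participation in the study, they will be withdrawn from the study".
- **After exit.** The same section promises an effort to obtain final-visit observations, worded for a subject who decides to withdraw. Withdrawn subjects are not replaced.
- **Treatment.** In the Study Arm "the subject will receive one session of cryoanalgesia" (section 5.2.2). Section 5.1 restricts the term index procedure to use of the cryoICE system; section 7.2 applies it to both arms.
- **Analysis.** The ITT population in section 9.5 is those randomised "on whom the surgical index procedure is attempted (even if the index procedure is aborted". Section 9.6.1 compares 48-hour means by t-test. Section 9 says nothing about missing values.
- **Deviations and safety.** Section 8.2.2 gives "Developed withdrawal criteria during the study, but not removed" as a possible deviation category. Section 10.2.4 has unresolved SAEs followed "until the events are resolved, or the subject has exited the study", or until otherwise explained.

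**The concern.** In a drug trial, stopping treatment and leaving the study are separate events. Here treatment is over before the patient leaves the operating room, so an exit for a failed device or procedure protects nobody from further study treatment. Its only effect is to stop the measurements.

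The reason is also tied to one arm. A subject who never receives cryoICE cannot have a cryoICE failure. If failed ablations are exited on the day of surgery, the Study Arm mean at 48 hours comes from the procedures that worked, while the Control Arm mean comes from everyone available. Both co-primary comparisons would then drift from the effect of assigning cryoanalgesia towards its effect when the ablation succeeds. Failure plausibly goes with worse pain control: Appendix 3 describes it as "Failure to ablate peripheral nerve may result patient requiring pain management".

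**Working it through.** **Inputs.** From section 9.3: 75 and 25 subjects; FEV1 difference 0.26, SD 0.39; VAS difference 1.8, SD 2.2; two-sided alpha 0.05; equal-variance t-test; no dropout allowance. The documents give no withdrawal rate. Appendix 3 places device breakage and failure to ablate in its more-than-10% risk band.

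**The plan's own power.** Noncentrality = D / (SD × √(1/75 + 1/25)), with √(1/75 + 1/25) = 0.2309.
- FEV1: 0.26 / (0.39 × 0.2309) = 2.89, power 81.6% (stated 80%).
- VAS: 1.8 / (2.2 × 0.2309) = 3.54, power 93.9% (stated 94%).

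Both reproduce.

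**How a failed procedure could leave the comparison.**
1. Failure occurs in theatre (5.1, 5.2.2), before 48 hours.
2. Section 4.2.5 permits it as a reason for exit.
3. Section 9.5 still counts the subject in ITT.
4. Section 7.3 lists neither spirometry nor VAS at 24 hours, so the visit schedule gives no post-operative value of either measure before 48 hours. (Section 9.6.1 mentions hourly VAS on the day of surgery, but no visit lists it.)
5. The t-test uses observed values only, so the subject is in the population but not in the test.

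**Scenario 1: a real effect, but none in failures.** Assume a fraction f of the Study Arm fails, has the Control Arm mean, and is all exited before 48 hours. The effect in all randomised is (1 − f) × D, the effect after removal is D, and the overstatement is 1/(1 − f) − 1. Power is by exact t with the SD unchanged; 8 of 75 are removed at 10% and 15 at 20%.

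| f | FEV1, all kept | VAS, all kept | Excess after removal (FEV1; VAS) | Overstatement | Power, all kept (FEV1; VAS) | Power after removal (FEV1; VAS) |
|---|---|---|---|---|---|---|
| 5% | 0.247 | 1.71 | 0.013; 0.09 | 5% | 77.5%; 91.5% | 81.0%; 93.6% |
| 10% | 0.234 | 1.62 | 0.026; 0.18 | 11% | 73.0%; 88.4% | 80.3%; 93.2% |
| 20% | 0.208 | 1.44 | 0.052; 0.36 | 25% | 62.8%; 80.1% | 79.0%; 92.5% |

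**Scenario 2: no true effect.** If the removed fraction f lies s SD worse than the arm mean, the bias is f × s / (1 − f) SD.
- s = 0: no bias; the chance of a significant result favouring cryoanalgesia stays at 2.5%.
- f = 10%, s = 0.5 to 1: 0.056 to 0.111 SD, or 0.12 to 0.24 VAS points; that chance becomes 4.2% to 6.8%.
- f = 20%, s = 0.5 to 1: 0.125 to 0.25 SD, or 0.28 to 0.55 VAS points; 7.5% to 17.8%.

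**The case against.** The case against has real force, and several stronger readings that a reader might infer are not supported.

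- **That the clause removes failures and so biases the trial.** Section 4.2.5 only says what reasons may be recorded. It does not say that a device failure ends participation, or when. Section 9.5 and the sentence in 4.2.5 keeping subjects not extubated or discharged by Day 5 in follow-up both point towards retention. This stands: the documents show a permitted route, not an operating rule.
- **That loss is one-sided throughout.** Adverse events, deviations and sponsor recommendation can apply in either arm. Only device or index procedure failure is specific to the Study Arm, and that rests on section 5.1; section 7.2 uses the term for both arms.
- **That section 8.2.2 compels removal.** It gives examples of categories for summarising deviations, and 4.2.5 does not define device failure as requiring exit.
- **That about 8 of 75 would be withdrawn.** The more-than-10% band is a general risk statement. The consequence it names for failed ablation is pain management, not exit.
- **That type I error is clearly inflated.** If cryoanalgesia does nothing, a failed ablation does not itself change pain, so s above zero needs another link between failure and outcome. The documents supply none.
- **That allodynia would be understated.** Section 10.0 attaches nerve damage and neuralgia to the cryoablation itself, so failed ablations might carry less of that risk. The direction is unknown.

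Section 9.7 also allows a later detailed analysis plan, but only if needed and with no commitment on missing data. What the objections leave untouched is that no text secures the 48-hour values after exit, and ITT membership cannot supply them.

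**Conclusion.** The gap is real, as a permitted risk and not a demonstrated bias. After a one-session treatment the plan allows exit for a reason that, on the section 5.1 definition, exists only in the Study Arm and arises before both co-primary endpoints. It neither secures nor handles the values lost, so the intention in section 9.5 to count aborted procedures can be defeated by missing data.

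The direction favours cryoanalgesia only if those exited do worse than the rest of their arm. The 11-25% figure needs three assumptions together: 10-20% of the Study Arm fails, failures gain nothing, and all are exited before 48 hours. None is given in the documents. The point deserves correction because the correction is cheap and the endpoints are co-primary, not because a large bias has been shown.

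**What to change.** 1. In 4.2.5, remove device or index procedure failure, protocol deviation and sponsor recommendation as reasons to end participation. State that they are recorded, that the subject stays in scheduled assessments, including 48-hour FEV1 and VAS, through Day 180, and that the subject is analysed in the randomised arm.
2. Align the 8.2.2 deviation category with this.
3. Reconcile the use of index procedure in 5.1, 7.2 and 9.5. Read literally with 5.1, no control subject can meet the ITT condition.
4. Prespecify in section 9 how missing 48-hour values are handled, with a sensitivity analysis: for example, assign Study Arm subjects missing after a failed procedure the Control Arm mean, then progressively worse values until the conclusion changes.
5. Leave the best-interest withdrawal decision for adverse events as it is. Sections 4.2.5 and 10.2.4 should be reconciled on whether data collection and SAE follow-up continue after such a withdrawal where consent allows.

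**Cost.** Protocol wording, plus a few in-hospital assessments and later contacts. If failures gain no benefit, the estimated effect is smaller and power lower: for FEV1 about 73% at 10% failures and 63% at 20%. The sponsor should weigh that when confirming the sample size. Retention does not cure missingness from withdrawn consent, death or inability to perform the tests, which is why item 4 is needed as well.

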5.0 PROCEDURE

5.1 General Description

Individual centers and investigators will be selected based upon their expertise in unilateral thoracotomy cardiac procedures as well as proficiency in cryoanalgesia using the AtriCure® *cryoICE* cryo-ablation system.

The protocol term “index procedure” refers only to the use of the *cryoICE* system. All procedures leading up to and after the use of the *cryoICE* system are considered part of the unilateral cardiac thoracotomy procedure and are to be conducted under the discretion of the surgeon in accordance to the hospital’s standard of care.

If the subject meets all study eligibility criteria, they will be enrolled and randomized. If the subject is randomized to the group to receive the Intercostal Analgesia by using the AtriCure® *cryoICE* cryo-ablation system, the following steps are performed:

*Note: A recommended surgical technique is presented below. It is recognized that individual patient anatomic variation, surgical conditions, or surgeon preference may necessitate modifications to the outlined procedures. Regardless, surgeons must adhere to the instructions for use for the AtriCure *cryoICE* Probe (CRY02) as outlined in the IFU.*

5.2 Intercostal CryoAnalgesia (Index Procedure)

5.2.1 Control Arm – Surgery without Intercostal Cryoanalgesia + standard POPM

If the subject is randomized to the Control Arm, the subject will receive post-operative pain management as prescribed by the attending physician or institutional standard for post-operative unilateral thoracotomy cardiac surgery patients.

5.2.2 Study Arm – Surgery with Intercostal Cryoanalgesia + standard POPM

If the subject is randomized into the Study Arm, the subject will receive one session of cryoanalgesia

5.2.3 Pain Management for Both Treatment Groups

Pre-operative:

Institutional SOC for pain management will be followed for both study groups in the pre-operative phase.

Intra-operative:

All non-invasive and invasive monitoring, induction of general anesthesia and oral endotracheal intubation will be provided per institutional protocol. All anesthetic techniques, intraoperative TEE examinations, surgical procedures, CPB, and vasoactive infusions in terminating CPB are not impacted by this protocol. The study group and control group will receive treatment as previously outlined.

Post-Operative:

Post -operative pain management will be managed according to the institutional standard of care. The decision to administer additional pain management therapy in the post-operative/follow-up setting is left to the discretion of the Investigator, and his/her assessment of the patient's pain level. All medications taken for all pain management will be captured and recorded in the subject's source documents and on the eCRF.

The use of local post-operative pain management techniques (i.e., intercostal, peri-vertebral, or any other acceptable method) is permitted for both treatment groups up to 24 hours post-operatively according to institutional standard of care.

6.0 IDENTITY OF STUDY DEVICES

The devices utilized for the study include:

The AtriCure® cryoICE cryo-ablation system

A large rectangular area of the page is heavily redacted with black ink, obscuring a list of study devices. The redaction is approximately 450 pixels wide and 350 pixels high, starting below the text "The AtriCure® cryoICE cryo-ablation system".

All medical devices used during this study are cleared for commercial distribution and are to be used in accordance with approved product labeling.

6.1 Product Accountability

Product accountability will not be applicable as the investigator will use commercially available products for this study. Devices will not be provided by the sponsor.

7.0 SUBJECT VISITS

Details for specific subject visit activities are found below and reflect the Schedule of Assessments grid.

7.1 Visit 1 – Baseline

Subjects will be screened for study participation during the baseline visit. The procedures required for the baseline visit may be conducted during more than one visit. The following will be conducted and/or obtained: Some baseline procedures may have been completed as patient standard of care and therefore may be completed prior to informed consent and do not need to be repeated after consent.

The following procedures must be conducted within 30 days prior to the index procedure:

- Informed Consent
- Demographics
- Medical and Surgical History
- Targeted Physical Exam
- Pregnancy Test, as required (within 7 days of procedure)
- Vital Signs
- Height and Weight
- Spirometry
- Concomitant Medication Review
- Inclusion/Exclusion Criteria
- Randomization
- VAS
- Ambulatory Movement

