4.2.2 Enrollment

Patients are considered **enrolled** in the study once they have met Inclusion/Exclusion criteria and are randomized.

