4.2.4 Exclusion Criteria

Patients satisfying the following criteria will not be eligible for participation:

1. Cardiac valve surgical procedure via conventional full sternotomy
2. Procedures that require a posterolateral thoracotomy
3. Current pregnancy
4. Current use of prescription opioids
5. FEV1 < 40% predicted
6. Documented myocardial infarction within 30 days of signing informed consent
7. Documented psychiatric disease
8. Documented chronic pain syndrome
9. Documented history of substance abuse
10. Patient currently enrolled in another research study that could directly affect results of either study
11. Physical or mental condition that would interfere with patient's self-assessment of pain
12. A medical condition that in the investigator's opinion could adversely impact the patient's participation or safety, conduct of the study, or interferes with the pain assessments

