9.4 Randomization

Upon enrollment, subjects will be assigned a sequential identification number at each site and a corresponding sealed envelope which will be opened prior to the procedure to reveal the treatment group. Subjects will be randomized 3:1 (3 intercostal Cryoanalgesia in conjunction with SOC and 1 SOC). Randomization sequences will be generated by AtriCure Statistician using SAS version 9.4 (SAS Institute Inc., Cary, North Carolina) and will be stratified by site.

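### Randomization is listed as a baseline task up to 30 days before the index procedure and the envelope has no earliest opening time, so the arm may be known while analgesia is planned and before patients drop out ahead of surgery

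*Combined protocol and SAP*

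**What the plan says.** **Timing.** Protocol section 7.1 (Visit 1, Baseline) opens its list with "The following procedures must be conducted within 30 days prior to the index procedure", and Randomization is one of the items. It does not appear on the Visit 2 list in section 7.2. Section 4.2.2 counts patients as enrolled "once they have met Inclusion/Exclusion criteria and are randomized". Under sections 4.1 and 9.4 the enrolled subject then receives a sequential number and "a corresponding sealed envelope which will be opened prior to the procedure to reveal the treatment group". The available text gives no earliest opening time, names no one to open the envelope, and does not say who may learn the arm.

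**Analgesia.** Section 5.2.3 sets no regimen. Before surgery, "Institutional SOC for pain management will be followed for both study groups in the pre-operative phase". Anesthetic technique follows the institution, and additional post-operative treatment is at the investigator's discretion. Local techniques such as intercostal or peri-vertebral methods are an option whose use "is permitted for both treatment groups up to 24 hours post-operatively according to institutional standard of care". Section 5.2.1 leaves control-arm analgesia to the attending physician or the institutional standard.

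**Blinding.** The synopsis calls the study blinded. The only people the text says should be blinded are the person conducting the VAS and the person administering the allodynia test (section 7.11).

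**Analysis.** Section 9.6.1 compares 48-hour FEV1 and VAS means by t-test without covariates. Section 9.5 restricts the ITT population to randomized subjects in whom the surgical index procedure is attempted. Section 5.1 says that the term index procedure "refers only to the use of the" cryoICE system.

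**The concern.** Objective 1 is a claim about what intraoperative cryoanalgesia adds to standard care. The comparison isolates that effect only if the rest of the analgesic care is chosen in the same way in both arms. A team that knows ahead of time who will not receive cryoanalgesia can plan more regional or systemic analgesia for that patient, which hides benefit. It can also plan more for the study arm, which creates apparent benefit. An unadjusted t-test passes either imbalance straight into both co-primary contrasts.

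The second consequence concerns who is analyzed. The longer the interval between randomization and surgery, the more patients are cancelled or have their operation changed after allocation. Under section 9.5 these patients can drop out of the analysis. If the arm is already known, their loss need not be independent of it. Section 4.2.5 does not replace subjects who withdraw, and the control arm has only 25.

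**Working it through.** **1. Reproduce the plan's power (section 9.3).** Inputs: 75 study and 25 control subjects, two-sided alpha 0.05, equal-variance t-test; FEV1 difference 0.26 with SD 0.39; VAS difference 1.8 with SD 2.2.

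Standard error = SD × √(1/75 + 1/25); noncentrality = difference / standard error; df = 98; critical t = 1.984.

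| Endpoint | SE | Noncentrality | Power | Plan states |
|---|---|---|---|---|
| FEV1 | 0.0901 | 2.887 | 81.6% | 80% |
| VAS | 0.508 | 3.543 | 93.9% | 94% |

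Both stated figures reproduce to within two percentage points.

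**2. What an arm-dependent shift would do.** The documents give no rate of regional technique use by arm and no effect of such a technique at 48 hours. The shift b below is therefore an assumption, shown over a range, and is not an estimate. The same formula is used with b in place of the difference (no true effect), or with the planned difference minus b (shift masking part of a true effect).

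| Endpoint | Assumed shift b | Rejection rate, no true effect | Power, planned difference minus b |
|---|---|---|---|
| VAS | 0.25 | 7.8% | 85.6% |
| VAS | 0.5 | 16.4% | 71.7% |
| VAS | 1.0 | 49.6% | 34.5% |
| FEV1 | 0.05 | 8.5% | 63.6% |
| FEV1 | 0.10 | 19.6% | 42.0% |

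Example: for a VAS shift of 0.5, noncentrality = 0.5 / 0.508 = 0.984, and the nominal 5% test rejects 16.4% of the time.

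**3. What losses before surgery would do.** Each control lost is 1/25 = 4% of that arm. FEV1 power is 80.4% with 75 v 24 and 79.1% with 75 v 23. If about 5% or 10% of the study arm leaves instead (71 v 25 or 67 v 25), it is 81.0% or 80.3%. Lost numbers alone therefore cost little power. The risk is that losses are related to a known arm.

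**4. Whether anything in the text closes the gap.** Section 7.1 places the task at baseline, section 7.2 does not move it to the day of surgery, and sections 4.1 and 9.4 set only a latest time for opening. Section 5.2.3 neither fixes the analgesic plan in advance nor conceals the arm from prescribers. Pain medication is captured on the eCRF and opioid consumption is a secondary endpoint, so an imbalance could be described afterwards. The co-primary tests would not account for it.

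**The case against.** The strongest reply is that assignment and disclosure are separate steps. A sealed envelope can be allocated at Visit 1 and stay sealed until the day of surgery, and 30 days is an outer limit for a list that may span several visits. This is right: a reader might infer that the protocol authorizes early opening, but it only fails to prevent it. Two places that might hold a timing rule, the Schedule of Assessments grid and most of section 5.2.2, are also missing from the available text.

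Several stronger readings are tempting and are not supported:

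- *Baseline VAS is taken after allocation and so biases the result.* The order of bullets in section 7.1 is not a stated sequence, and baseline VAS does not enter the 48-hour t-test.
- *Regional blocks in controls would cut VAS power to a particular figure.* This needs an assumed block effect at 48 hours. Section 5.2.3 allows local techniques only to 24 hours, and section 1.0 describes intercostal blocks as short lived.
- *Converted study-arm patients dilute the FEV1 effect.* If index procedure means cryoICE use (section 5.1), a patient in whom it is never attempted leaves the ITT population and does not dilute the mean.
- *Eligibility by approach is settled only in the operating room.* The documents do not say so. An exclusion such as "Procedures that require a posterolateral thoracotomy" can be applied to the planned operation, and section 4.1 requires eligibility before randomization. No conversion or cancellation rate is given.

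Some protection already exists: a common institutional standard for both arms, stratification by site and a blinded VAS assessor. These reduce the risk. They do not stop a prescriber who knows the arm from acting on it. It is also true that the surgeon learns the arm eventually, so late opening cannot control post-operative choices.

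**Conclusion.** The point holds as a weakness in allocation timing. As written, the plan permits the arm to be known well before surgery, in a trial where analgesia is discretionary and the primary tests are unadjusted. The resulting bias could run in either direction on 48-hour VAS and FEV1. Early randomization also enlarges the group that can leave the ITT population before an attempted procedure.

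The size cannot be derived from the documents. The 16% rejection rate for a 0.5-point VAS shift rests entirely on that assumed shift and shows sensitivity only. The conclusion also assumes that the missing grid and the missing part of section 5.2.2 contain no rule on envelope timing. If they do, sections 4.1, 7.1 and 9.4 need only be aligned with it. The change is worth making because it is cheap, although there is no evidence that sites would in fact open envelopes early.

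**What to change.** 1. Move Randomization from the Visit 1 list (section 7.1) to Visit 2 (section 7.2).
2. State in sections 4.1, 7.2 and 9.4 that the next envelope is opened in the operating room, as late as practicable before the point of cryoanalgesia, once eligibility has been re-confirmed and the pre-procedure VAS and intended analgesic and regional plan are on the eCRF.
3. Log the opening time, and tabulate regional technique use by arm in the report.
4. Leave the permitted analgesia as it is.

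The cost is a few sentences of protocol text, eCRF entries for the plan and the opening time, and having the cryoanalgesia equipment ready for every case, including those that turn out to be controls. The change protects pre-operative and intra-operative planning only. Post-operative departures from the recorded plan become visible but are not prevented.
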